5.2 Exclusion Criteria

A patient will not be eligible for this study if any of the following exclusion criteria are met.

- 5.2.1 Prior hormonal therapy for metastatic disease (prior adjuvant tamoxifen or aromatase inhibitor will be allowed)
- 5.2.2 Prior chemotherapy for metastatic disease
- 5.2.3 Prior treatment with sorafenib
- 5.2.4 Patients with a history of brain metastases or leptomeningeal metastases.
- 5.2.5 Second primary malignancy except most situ carcinoma (e.g. in situ carcinoma of the cervix, adequately treated non-melanomatous carcinoma of the skin) or other malignancy treated at least 5 years previously with no evidence of recurrence
- 5.2.6 Cardiac disease: Congestive heart failure > class II NYHA (see Appendix B). Patients must not have unstable angina (anginal symptoms at rest) or new onset angina (began within the last 3 months) or unstable coronary artery disease within the past 6 months
- 5.2.7 Serious concomitant systemic disorders (including symptomatic congestive heart failure, unstable angina pectoris, cardiac arrhythmia requiring therapy, myocardial infarction within the past 6 months, or active infections or severe hepatic impairment) that would compromise the safety of the patient or compromise the patient's ability to complete the study, at the discretion of the investigator
- 5.2.8 Uncontrolled hypertension defined as systolic blood pressure > 150 mm Hg or diastolic pressure > 100 mm Hg, despite optimal medical management
- 5.2.9 History of allergic reactions attributed to compounds of similar chemical or biologic composition to letrozole or sorafenib
- 5.2.10 History of allergic reaction to sulfonamides
- 5.2.11 Thrombolic or embolic events such as a cerebrovascular accident including transient ischemic attacks within the past 6 months
- 5.2.12 Serious non-healing wound, ulcer, or bone fracture
- 5.2.13 Evidence or history of bleeding diathesis
- 5.2.14 Major surgery, open biopsy or significant traumatic injury within 4 weeks of first study drug
- 5.2.15 Use of cytochrome P450 enzyme inducing antiepileptic drugs (phenytoin, carbamazepine, or phenobarbital), or St. John's Wort or rifampin (rifampicin)
- 5.2.16 History of malabsorption syndrome
- 5.2.17 Patients with immune deficiency are at increased risk of lethal infections when treated with marrow-suppressive therapy, therefore, known HIV-positive patients receiving combination anti-retroviral therapy are excluded from the study because of possible pharmacokinetic interactions with sorafenib.

Phase I/II Trial of	and	First-Line Therapy in Postmenopausal
Women with Hormone Rece	eptor-Positive Locally Advar	nced or Metastatic Breast Cancer

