Therefore, one way to enhance endocrine sensitivity and delay disease progression in patients with hormone receptor-positive metastatic breast cancer is to add an anti-VEGF therapy, such as an oral tyrosine kinase inhibitor of VEGF, to standard anti-hormonal treatment for patients with breast cancer. In this trial, we will test the hypothesis that adding an anti-angiogenic agent might delay the onset of resistance to endocrine therapy, specifically estrogen deprivation with an aromatase inhibitor.

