Thus, it is also a highly selective inhibitor of aromatase. The high potency and selectivity of letrozole explains its favorable pharmacological profile and high therapeutic index. In postmenopausal patients with advanced breast cancer, daily doses of 0.1 to 5 mg letrozole suppressed plasma levels of estradiol, estrone and estrone sulfate by 75-95% from baseline.¹⁴

- 2.1.2.2 Clinical Information: A Phase III global, multicenter, randomized clinical trial evaluated letrozole (2.5 mg/day) as a first-line hormonal therapy as compared to the present standard of treatment tamoxifen (20 mg/day).8 This trial accrued 907 postmenopausal women with ER and/or PR positive or unknown receptor breast cancer and locally advanced disease, metastatic disease, or loco-regional recurrence not amenable to treatment by surgery or radiotherapy. Patients received treatment until disease progression or discontinuation for any other reason. The primary endpoint was time to progression (TTP). Letrozole was superior to tamoxifen and reduced the risk of progression by 28% (hazard ratio 0.72, P < .0001). The median TTP was prolonged by 57%: 6.0 months for tamoxifen vs. 9.4 months for letrozole. The secondary endpoints included overall tumor response rate, clinical benefit, and time to treatment failure. Overall tumor response rate (complete and partial response) was significantly higher with letrozole (32% vs. 21%, P = .0002), irrespective of dominant site of disease. Clinical benefit (complete response, partial response or stabilization of disease) lasting at least 24 weeks was 50% for letrozole vs. 38% for tamoxifen (P = .0004). Time to treatment failure was significantly better for letrozole compared to tamoxifen (9.0 months vs. 5.7 months respectively, P = .0001.) The median overall survival was slightly prolonged for letrozole vs. tamoxifen (34 months vs. 30 months, respectively). This difference is not significant. However, the study design included a crossover to the other treatment arm at the discretion of the investigator. An analysis was done in the patients who did not crossover, which demonstrated a 15-month survival advantage in the letrozole treatment group. 15 The data cutoff for this analysis was September 2001 when median follow-up was 32 months with a maximum observation period of 57 months. Tolerability was similar in both arms of the trial, with 2% of patients on letrozole and 3% of patients on tamoxifen discontinuing therapy due to adverse events.

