16.2 Sample Size Justification

A historical study showed that single-agent letrozole in the first-line treatment of patients with hormone receptor-positive metastatic breast cancer had a clinical benefit rate of 50% compared to tamoxifen. The combination therapy of letrozole and sorafenib will not be considered of further interest if the true clinical benefit rate is less than or equal to 50%. We assume that this study will target a clinical benefit rate of 67% for identifying the combination therapy as active and worthy of further investigation. With these settings, the null hypothesis is that the clinical benefit rate of the combination therapy is less than or equal to 50%, and the alternative hypothesis is that the clinical benefit rate of 67% or more is of considerable interest. For the phase II part of the study, the sample size was calculated according to a single-stage design. The study will accrue a total of 58 patients, and the combination therapy will be accepted if there are at least 35 responders out of 58 patients. The design will have a 4.3% (< 5%) type-I error (false positive) rate and a power of 82.7% (> 80%) (i.e., 17.3% type-II error or false negative rate). The total number of evaluable patients to be accrued to this study is not expected to exceed 64 patients.

Phase I/II Trial of Letrozole (and Sorafenib as First-Line Therapy in Postmenopausal Women with Hormone Receptor-Positive Locally Advanced or Metastatic Breast Cancer PI:

The patients accrued in the Phase I dose escalation will be included in the Phase II portion if they receive the same dose. Evaluable patients for the phase I portion are defined as study-eligible patients who have received at least one cycle of treatment. Evaluable patients for the phase II portion are those who have received at least two cycles of treatment.

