17.1 Subject Population

Postmenopausal women with previously untreated hormone receptor-positive locally advanced or metastatic breast cancer may participate in this trial if they meet the eligibility criteria. The inclusion and exclusion criteria detailed in this protocol are designed to exclude patients solely for medical reasons. Study participants will be patients who are receiving care for their disease at the affiliated medical oncology practices and community hospitals. The Principal Investigator and OHRS research personnel will closely monitor the status of the study (and individual patient data) at all centers. Males will not be eligible for this study. Breast cancer in men is rare and the efficacy of aromatase inhibitors in males is limited.

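### Women with prior adjuvant aromatase inhibitor are tested in one group against a 50% benchmark not shown to apply to them, so power may be lower than stated and a negative result would be ambiguous

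*Combined protocol and SAP*

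**What the plan says.** Section 5.2.1 lists as an exclusion "Prior hormonal therapy for metastatic disease (prior adjuvant tamoxifen or aromatase inhibitor will be allowed"). It sets no minimum time since the last adjuvant dose, no restriction on relapse during treatment and no cap on numbers. Section 17.1 describes the population differently: "Postmenopausal women with previously untreated hormone receptor-positive locally advanced or metastatic breast cancer may participate". It does not say how that label fits with permitted adjuvant therapy.

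In section 16.2, "the null hypothesis is that the clinical benefit rate of the combination therapy is less than or equal to 50" per cent, and on the alternative, "We assume that this study will target a clinical benefit rate of 67" per cent. The combination is accepted with at least 35 responders among 58, with a stated type I error of 4.3% and power of 82.7%. Sections 16.3 and 16.4 plan no breakdown by prior therapy.

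The 50% comes from the randomised letrozole versus tamoxifen trial in section 2.1.2.2: "Clinical benefit (complete response, partial response or stabilization of disease) lasting at least 24 weeks was 50% for letrozole vs. 38% for tamoxifen". On its timing: "The data cutoff for this analysis was September 2001 when median follow-up was 32 months with a maximum observation period of 57 months". The protocol does not report adjuvant AI exposure in that trial.

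**The concern.** A woman whose cancer recurs while she is taking adjuvant letrozole can be enrolled and given letrozole again with sorafenib. Section 2.1 states the hypothesis that "adding an anti-angiogenic agent might delay the onset of resistance to endocrine therapy". For her the question is closer to whether resistance can be reversed. If the benchmark trial enrolled few such women, 50% may not be what letrozole alone would achieve in the mix this trial enrols.

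The test drives a go/no-go decision, since at a true rate of 50% or less the combination is of no further interest. A lower rate in AI-relapsed women would pull the overall rate down by an amount set by recruitment rather than by sorafenib. With no planned breakdown, any later attempt to separate the two explanations would be post hoc.

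**Working it through.** **1. The plan's own figures.** Exact binomial with n = 58, null 0.50 and alternative 0.67 (section 16.2):

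- At least 35 of 58, as printed: P(X ≥ 35 | 0.50) = 7.4%; P(X ≥ 35 | 0.67) = 88.7%.
- At least 36 of 58: P(X ≥ 36 | 0.50) = 4.3%; P(X ≥ 36 | 0.67) = 82.6%.

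The stated 4.3% and 82.7% therefore belong to at least 36, not to the printed at least 35. That mismatch needs reconciling in its own right. Both cut-offs are carried below.

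**2. How far the benchmark reaches.** September 2001 minus 57 months is December 1996, so the benchmark trial's first patient entered about then. The adjuvant AI trial in the protocol's reference list is a first-results report from 2002. From these dates I infer little adjuvant AI exposure in the benchmark trial; the documents do not state it.

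**3. Effect of a mixed population.** Let f be the share of the 58 who relapsed on an adjuvant AI and q their clinical benefit rate on the combination. Assume 67% holds in everyone else. The overall rate is p = (1 − f) × 0.67 + f × q; for example, 0.90 × 0.67 + 0.10 × 0.50 = 0.653. Power is P(X ≥ r | 58, p). Both f and q are assumptions.

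| f | q | p | Power, ≥ 36 | Power, ≥ 35 (printed) |
|---|---|---|---|---|
| 0% | – | 0.670 | 82.6% | 88.7% |
| 5% | 50% | 0.6615 | 78.8% | 85.8% |
| 10% | 50% | 0.653 | 74.6% | 82.4% |
| 10% | 30% | 0.633 | 63.3% | 72.9% |
| 20% | 60% | 0.656 | 76.1% | 83.7% |
| 20% | 40% | 0.616 | 52.9% | 63.3% |
| 20% | 30% | 0.596 | 40.5% | 51.1% |

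If q is 67%, nothing is lost.

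**4. Share at which power reaches 70%.** At ≥ 36, 70% power corresponds to p = 0.6444, so f = (0.67 − 0.6444)/(0.67 − q): about 15% for q = 50%, 9.5% for q = 40% and 7% for q = 30%. At ≥ 35 the corresponding p is 0.6276, and the shares are about 25%, 16% and 11.5%.

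**5. What a comparison in unexposed women could deliver.** With 20% exposed, about 46 women remain (58 × 0.80 = 46.4). The smallest cut-off with one-sided alpha of at most 5% is 30 of 46, with power 66.6% at 67%. With 10% exposed, about 52 remain (58 × 0.90 = 52.2); the cut-off is 33 of 52 and power is 75.8%.

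**The case against.** A reader might infer that the design loses much of its stated power and that a negative result cannot be interpreted. The documents support neither. The size of the loss needs a share and a rate that they do not give, and mild inputs cost little: with 10% of women at a 50% rate, the printed rule keeps 82.4% power, practically the stated figure. A negative result would be ambiguous rather than unreadable, and reporting by exposure would partly resolve it. A positive result stands on this point, because a subgroup with a lower rate makes the test against 50% harder to pass.

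Nor may one presume that these women do badly. Section 2.1 also speaks of enhancing endocrine sensitivity, and section 2.1.3.1 says that endocrine-resistant ER-positive cells depend more on MAPK signalling, which sorafenib targets. The benchmark was not a selected AI-sensitive population either: half its letrozole patients had no clinical benefit. Some differences may push the other way. Of the benchmark, section 2.1.2.2 says "This trial accrued 907 postmenopausal women with ER and/or PR positive or unknown receptor breast cancer", whereas section 5.1.3 requires receptor-positive disease. The two-cycle evaluability rule also removes women who stop early.

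It is not shown that AI history goes unrecorded. Section 5.6 requires an eligibility checklist and section 6 a baseline history; eCRF content sits in a data capture plan that is not among the documents.

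Finally, restricting the comparison to unexposed women is no cure-all. With 20% exposed at a 50% rate, the pooled test at ≥ 36 has 65.1% power against 66.6% in the unexposed. The gain is real only when the exposed rate is low: at 30%, 40.5% against 66.6%.

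All of this limits the size of the point. None of it shows that 50% applies to AI-exposed women, or supplies a planned analysis by exposure.

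**Conclusion.** The point holds as a gap in the analysis plan. AI-exposed women are eligible without any interval and are pooled in a test against a benchmark not shown to describe them. If those who relapsed on an AI have a benefit rate below 67% on the combination, power falls, and a failure to reach the cut-off could reflect case mix rather than sorafenib.

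Across the assumed inputs the loss runs from small to severe: from 82.6% to between 78.8% and 40.5% at ≥ 36, and from 88.7% to between 85.8% and 51.1% at the printed ≥ 35. This rests on assumed shares of 5–20%, assumed rates of 30–60%, 67% in all other women, and the inference from dates in step 2. It is a cheap improvement worth making, not a flaw that invalidates the design.

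**What to change.** Leave eligibility and the all-patient primary test unchanged, and:

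- confirm that prior adjuvant AI and the date of its last dose are captured at baseline;
- in 16.3 and 16.4, prespecify the clinical benefit rate with exact confidence intervals by prior AI exposure (none, relapsed on treatment, relapsed later), with the comparison to 50% in unexposed women as supportive only;
- in 16.2, first reconcile the cut-off with its error rates, then state that the power figure assumes a 67% rate across the whole enrolled mix, and give the range for the agreed cut-off.

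The cost is at most two baseline fields and a few sentences. The unexposed comparison is less precise (about 67% power with 46 women, 76% with 52), and it sets aside women who finished an AI long ago and may still be sensitive, which is why it should be supportive only. The stated power will also look less favourable.

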5.3 Inclusion of Women and Minorities

Women from all racial/ethnic groups are eligible for this study if they meet the eligibility criteria. Males will not be eligible for this study. Breast cancer in men is rare and the efficacy of aromatase inhibitors in males is limited.

5.4 Participation of Children

Only patients 18 years of age or older will be enrolled on this study, since postmenopausal breast cancer does not occur in children.

5.5 Sources or Methods of Recruitment

Patients will be recruited through screening of patients being followed in the

5.6 Study Enrollment Procedures

A copy of the institution's IRB-approved informed consent document and written justification for any changes made to the informed consent for this protocol must be on file at the before any participating institution may enter patients. Consent forms proposed for use at a participating institution must be reviewed and approved by the OHRS Regulatory Affairs Manager and all documents must be received (i.e., IRB approved documentation, IRB approved consent form, See Section 15.2 for a complete list of regulatory items).

Participating institutions will register patients through the OHRS Registration Desk

Patient demographic information, the signed and dated study-specific eligibility checklist and completed signature page of the consent form and additional source documents if requested by OHRS must be sent to the registration desk. Once the OHRS Registration Desk verifies eligibility, a unique patient study number will be issued. The patient will not be identified by name. This is the point that the patient is considered on study. Patients must not start protocol treatment prior to registration.

If a patient does not receive any protocol therapy, baseline data will be collected and submitted on the pre-study and follow-up electronic case report forms (eCRF). The reason for not starting protocol therapy will be documented in the "follow-up eCRF". Case report form completion instructions and training will be provided to each participating institution prior to study activation at the participating institution.

6. Study Parameters

The following tests and evaluations will be performed according to the schedule below. Baseline (i.e., pre-study) evaluations must be performed no longer than 4 weeks (+/- 3 days) prior to therapy, unless otherwise indicated in one of the footnotes below the table.

Evaluations	Pre- study	Every 4 weeks (prior to each cycle beyond cycle 1)	After the first 8 weeks (after first 2 cycles)	Every 12 Weeks	End of Treatment
Initial History and Physical	X ¹⁰				
Interim History and Physical ¹		X			X
Toxicity Assessment		X			X
ECOG Performance Status	X	X			X
Weight and Height ²	X	X			
CBC, differential, platelets	X^{10}	X ¹¹			X^{12}
Serum Chemistries ³	X^{10}	X ¹¹		***************************************	X^{12}
Liver Enzymes ⁴	X^{10}	X ¹²			X^{12}
EKG	X				
Radiographic Assessments ³	X			X	
Circulating Tumor Cells ⁶	X		X		
Correlative Blood Studies ⁶	X		X		
Archived Tumor Tissue ⁷	X				
Tumor Biopsy (if accessible)	X	Xg			
Pill Diary	***************************************	X			X
Record concomitant medications	X	X			X
Compliance Assessment		X			X
Survival 9					X

- Blood pressure should be monitored weekly during the first cycle. Measurements maybe obtained
 outside of the treating physician's office, however, must be documented in the patient's diary.
 Measurements should be made using a calibrated electronic device, unless performed in a doctor's office
 where a manual blood pressure measurement is acceptable.
- 2. Height to be measured only at baseline.
- Serum chemistries include: Sodium, Potassium, Chloride, Bicarbonate, Calcium, Glucose, BUN and Creatinine.
- 4. Includes: total bilirubin, AST, ALT, alkaline phosphatase, albumin and total protein.
- Radiographic assessments will be selected by the attending physician as clinically indicated and in accordance with the criteria for tumor measurement assessments. Confirmatory scans should be obtained ≤ 4 weeks following initial documentation of response. Response will be evaluated every 3 cycles.
- 6. See Section 11 for sample collection and analysis methods.
- 7. Obtain archived tumor tissue (from time of original diagnosis) for immunohistochemical analysis; can be obtained at anytime after enrollment. Send to Cancer Institute of New Jersey (see Section 11).
- 8. If biopsy is done, it should be performed prior to receiving study therapy and prior to start of Cycle 2. Send to see Section 11).

Phase I/II Trial of Letrozole and Sorafenib (as as First-Line Therapy in Postmenopausal Women with Hormone Receptor-Positive Locally Advanced or Metastatic Breast Cancer PI:

- 9. Follow every 3 months to determine status. A telephone call can be made for survival follow-up.
- 10. ≤ 14 days prior to treatment
- 11. \leq 7 days prior to re-treatment
- 12. As clinically indicated.

6.1 Efficacy Assessments

The primary efficacy endpoint is the clinical benefit rate of letrozole and sorafenib in this patient population. Clinical benefit rate ($CR + PR + SD \ge 6$ months) will be determined for each patient using definitions in RECIST to evaluate response.

will require copies of radiological scans performed during the study for all patients, and preferably on CD. A review of all radiological scans will be performed to verify or question the qualitative nature of the apparent response. For subjects with skin lesions, photographs should also be sent for review as well. Films and/or CDs should be mailed to:

7. Treatment Plan

7.1 General Considerations

Treatment will be administered on an outpatient basis. Patients will be instructed to start study drugs on Day 1 of each 28-day treatment period. One cycle is defined as 28 days of treatment. Prior to starting a cycle, all patients must continue to meet all inclusion criteria (see Section 5.1). No investigational or commercial agents or therapies other than those described below may be administered with the intent to treat the patient's malignancy. Patients will receive treatment until it is no longer of benefit to them. Patients may discontinue therapy at any time for any reason.

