5.1 Inclusion Criteria

A patient is eligible for enrollment if all of the following inclusion criteria are met.

- 5.1.1 Histologically confirmed invasive breast cancer
- 5.1.2 Stage IIIB, IIIC with T4 lesion or Stage IV disease
- 5.1.3 ER-positive and/or PR-positive of primary or secondary tumor tissue
- 5.1.4 Women age \geq 18 years
- 5.1.5 Postmenopausal status defined by one of the following criteria:
 - Age 56 or older and history of at least 12 months without spontaneous menstrual bleeding prior to study entry, or
 - Age 55 or younger with a history of at least 12 months without menstrual bleeding, whether spontaneous or from a prior hysterectomy, with a documented estradiol level within the institutional/laboratory postmenopausal range, or
 - Prior documented bilateral oophorectomy or
 - Ovarian suppression by a luteinizing hormone-releasing hormone (LHRH) agonist. Medical ovarian suppression can be initiated any time prior to or at the start of protocol therapy, and continued throughout the duration of the trial.
- 5.1.6 Patients must have an ECOG performance status 0, 1, or 2 (Appendix A).
- 5.1.7 Patients must have normal organ and marrow function as defined below:
 - ANC count $\geq 1200/\mu L$
 - Platelets $\geq 100,000 / \mu L$
 - Total bilirubin ≤ 1.5 X institutional ULN
 - AST(SGOT)/ALT(SGPT) ≤ 2.5 X institutional ULN, (≤ 5 X ULN if liver metastases present)
 - Creatinine ≤ 1.5 X institutional ULN
- 5.1.8 Patients can have non-measurable disease or measurable disease according to RECIST (Section 9).
- 5.1.10 Life expectancy of 3 months or longer

Phase I/II Trial of Letrozole and as First-Line Therapy in Postmenopausal Women with Hormone Recentor Positive Locally Advanced or Metastatic Breast Cancer PI: I

- 5.1.11 Able to swallow and retain oral medication
- 5.1.12 Written informed consent

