living	2 nd occurrence 3 rd occurrence	As for first occurrence, but upon resuming sorafenib treatment, decrease dose to the next lower dose level indefinitely Decision whether to discontinue sorafenib treatment should be made based on clinical judgement and patient preference

^{*}Patients who develop grade 3 fever/chills, grade 3 elevation of hepatic transaminases with ALT and AST < 10X ULN, grade 3 hyperlipasemia or hyperamylasemia without clinical or other evidence of pancreatitis, grade 3 leukopenia, or grade 3/grade 4 lymphopenia may continue study treatment without interruption at the discretion of the investigator.

Phase I/II Trial of Letrozole	and Sorafenib	as First-Line Therapy in Postmenopau	sal
Women with Hormone Receptor-Pos	ifive Locally Advance	ed or Metastatic Breast Cancer	
PI:			

Table 7.5.2.2 Dose Modification for Sorafenib Associated Non- Hematologic Toxicity

Toxicity	Grade 1	Grade 2	Grade 3	Grade 4
Non-	Continue at the	Continue at the	Withhold dose until	Withhold dose until
hematologic	same dose level.	same dose level.	toxicity is grade ≤ 1 ,	toxicity is grade ≤ 1 ,
			then resume treatment	then reduce dose to the
			at the same dose level.	next lower dose level
5-			If patient experiences	and resume treatment,
			a second grade 3	or discontinue at the
			toxicity, withhold	discretion of the
			dose until toxicity is	principal investigator
			grade ≤ 1 , then reduce	after discussion with
		* s (dose the next lower	study sponsor.
			dose level and resume	
			treatment.	If toxicity does not
				resolve within 2 weeks
			If toxicity does not	patient will discontinue
			resolve within 2	treatment.
			weeks patient will	
			discontinue treatment.	If a second toxicity
				occurs the patient will
				discontinue treatment.

Phase I/II Trial of Letrozole	and Sorafenib	as First-Line Therapy in Postmenopaus	al
Women with Hormone Receptor-Pos.	itive Locally Advanced	d or Metastatic Breast Cancer	
PI:			

Table 7.5.2.3 Dose Modification for Sorafenib Associated HematologicToxicity

Day 1 of Any Cycle	ANC < 1200/µL and/or platelets < 100,000 /µL	Hold Treatment
* CBCs should be repeated weekly until	If count recovers within 1 week	Resume treatment at full dose
recovery	If count recovers within 2 weeks	Reduce 1 dose level for all subsequent cycles
	If count does not recover within 2 weeks	Discontinue protocol treatment

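### Section 7.1 makes each cycle conditional on bilirubin and AST/ALT limits, but the schedule leaves on-treatment liver tests to discretion, so retreatment eligibility and symptom-free liver DLTs cannot be ascertained consistently

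*Combined protocol and SAP*

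**What the plan says.** **Retreatment.** Section 7.1: "Prior to starting a cycle, all patients must continue to meet all inclusion criteria", with a reference to Section 5.1. Item 5.1.7 includes "Total bilirubin ≤ 1.5 X institutional ULN" and "AST(SGOT)/ALT(SGPT) ≤ 2.5 X institutional ULN" (5 times ULN with liver metastases), besides ANC, platelets and creatinine.

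**Schedule.** In the Section 6 table, the column for visits before each cycle after the first has an entry for blood counts and for serum chemistries, each with footnote 11 (within 7 days before re-treatment). The row "Liver Enzymes" also has an entry there, but with footnote 12: "as clinically indicated". Footnote 4 puts bilirubin, AST and ALT in the liver panel. Footnote 3 defines the chemistry panel: "Serum chemistries include: Sodium, Potassium, Chloride, Bicarbonate, Calcium, Glucose, BUN and Creatinine".

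**DLT.** Section 7.4.1 counts Grade 3 or 4 non-hematologic toxicity in cycle 1. It excepts alopecia, and nausea and emesis that settle with symptomatic treatment. Laboratory findings are not excepted.

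**Dose modification.** The note under Table 7.5.2.1 lets the investigator continue treatment without a break in several situations. Among them are Grade 3 transaminase elevation with ALT and AST below 10 times ULN, and "grade 3 hyperlipasemia or hyperamylasemia without clinical or other evidence of pancreatitis".

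**The concern.** A mandatory condition for starting each cycle rests on a test that the schedule leaves to judgement. A site that follows footnote 12 literally can start a cycle with the 5.1.7 liver limits unchecked. A site that reads 7.1 as the controlling text will test every patient.

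The same gap reaches the phase I decision. A Grade 3-4 liver abnormality without symptoms in cycle 1 meets the DLT definition, but is counted only if someone draws the sample. In a 3+3 scheme a single patient matters. At either level, one DLT in three means expansion to six, while none in three means escalation (Level 0) or the recommended phase II dose (Level 1). Individual escalation from Level 0 to Level 1 for cycle 2 also depends on having had no cycle 1 DLT.

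**Working it through.** The plan states no figure on this point, so the check is mainly a side-by-side reading.

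**1. Is each 5.1.7 value scheduled before each cycle?**

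| Value in 5.1.7 | Row in the Section 6 table | Footnote before each later cycle |
|---|---|---|
| ANC, platelets | Blood counts | 11 (fixed window) |
| Creatinine | Serum chemistries | 11 (fixed window) |
| Bilirubin, AST/ALT | Liver | 12 (discretionary) |

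The chemistry panel lists eight analytes, none of them bilirubin, AST or ALT, so no other scheduled test fills the gap.

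**2. Is a liver test guaranteed for the DLT window?** The first scheduled on-treatment laboratory point is the one before cycle 2. With footnote 12 on the liver row, no liver value bearing on cycle 1 is guaranteed.

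**3. Does the note to Table 7.5.2.1 agree with 7.1?** The note's ceiling is 10 times ULN. The limits carried into 7.1 are 2.5 times ULN, or 5 times with liver metastases. A Grade 3 value above the applicable limit and below 10 times ULN may continue under the note but fails 7.1 when the next cycle is due. This conflict does not depend on any footnote mark.

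**4. Amylase and lipase.** Neither is in any row or panel, including baseline. Section 12.1 lists increases in both as very common (10% or more), and Section 17.2 names them when describing Grade 3-4 reactions. Neither is in 5.1, so the 7.1 rule does not depend on them. A laboratory-only event would enter the DLT count only if a test happened to be ordered.

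**5. Direction and scale of any under-detection.** At Levels 0 and 1 a dose passes with 0 DLTs in 3 patients, or 1 in 6. With p the *detected* DLT rate,

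P(pass) = (1 − p)³ + 3p(1 − p)⁵.

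For p = 0.33: 0.67³ + 3 × 0.33 × 0.67⁵ = 0.301 + 0.134 = 0.434.

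The documents give neither a DLT rate nor a missed share, so both are assumptions here. If a share m of DLTs is missed, p becomes the true rate × (1 − m):

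| True DLT rate (assumed) | none missed | 10% missed | 25% missed | 50% missed |
|---|---|---|---|---|
| 20% | 70.9% | 75.2% | 81.4% | 90.6% |
| 33% | 43.4% | 50.0% | 60.5% | 78.3% |

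Alternatively, assume a 20% rate of clinically evident DLTs plus a further rate x of patients whose only DLT is a laboratory finding:

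| x (assumed) | P(pass), all detected | P(pass), laboratory-only events unseen | P(at least one such event in 3 patients) |
|---|---|---|---|
| 2% | 66.5% | 70.9% | 5.9% |
| 5% | 60.0% | 70.9% | 14.3% |
| 10% | 49.4% | 70.9% | 27.1% |

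The last column is 1 − (1 − x)³. Section 12.1 gives transient transaminase increases as 1% to under 10% and bilirubin increase as 0.1% to under 1%. It does not split these by grade or by cycle, so they do not fix x.

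**The case against.** **The footnote mark may be wrong.** It is known here from a machine-read copy of the table, in which other marks are plainly misread: the radiographic row shows 3 where the note is 5, and a biopsy cell shows a letter where 8 is meant. If the liver row reads 11 in the original, the conflict between 7.1 and the schedule disappears. This stands as a condition on that part. It does not touch the note to Table 7.5.2.1 or the amylase and lipase point.

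**The rules can still be worked.** A reader might infer that the retreatment and DLT rules cannot be applied at all. The documents do not support that. The liver row has an entry in the four-weekly column, and a site can treat 7.1 itself as the indication. The DLT rule works for clinical toxicity, for hematology and for any value obtained. Section 8 requires a physician's toxicity assessment before each cycle and Section 17.2 mentions monthly blood work. Neither names an analyte, so they soften the gap without closing it.

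**Amylase and lipase are a lesser matter.** A reader might take their absence as a breach of the retreatment rule. It is not, since they are not inclusion criteria. The note that mentions them sits in the phase II section, is permissive, and operates on whatever value is available. Section 17.2 also describes the Grade 3-4 elevations as coming with symptoms of pancreatitis, which would tend to prompt a test. What remains is uneven detection of symptom-free events.

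**No undercount is shown.** This is correct. Section 17.2 calls Grade 3-4 reactions uncommon, and no rate of silent events is given.

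**Conclusion.** The point holds as a contradiction between passages that makes ascertainment inconsistent. If footnote 12 is the true mark, a liver condition that is mandatory in 7.1 rests on a discretionary test in Section 6, and symptom-free Grade 3-4 liver DLTs may or may not be found, depending on the site. The conflict between 7.1/5.1.7 and the note to Table 7.5.2.1 holds in either case. The absence of amylase and lipase is secondary and concerns the DLT count only.

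The ambiguity covers every patient at every cycle after the first, but that measures exposure to unclear instructions, not missed events. It would go too far to conclude that the phase I DLT count is too low or that the recommended dose is wrong. The documents support only the direction: any under-detection favors accepting a dose. The pass probabilities above rest on assumed rates and are for scale.

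**What to change.** First check the footnote mark on the liver row against the original table. Then reconcile four places: 7.1 with 5.1.7; the liver row of the Section 6 schedule (footnote 12 against 11); the DLT definition in 7.4.1; and the note to Table 7.5.2.1. The aim is that each laboratory value on which a retreatment or DLT rule depends is either scheduled, or no longer needed by the rule. The protocol should also say whether laboratory-only amylase and lipase events are meant to count as DLTs, and the schedule should match. Which testing or continuation rule is right is for the sponsor to decide.

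The cost is a footnote correction and some aligned wording, with at most added analytes on a blood draw already scheduled each cycle. Sample size and phase II analysis are unaffected.
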